## **6.3 Follow-up**

### **6.3.1 1 Month Phone Visit:**

- Changes in Concomitant Medications
- AE Assessment

### **6.3.2 3 and 12 Month In-Clinic Visits:**

- Changes in Concomitant Medications
- AE Assessment
- Physical Exam (including weight)
- Vital Signs (heart rate, blood pressure, oxygen saturation)

- Cardiac Markers (CRP, High Sensitivity Troponin T, NT-proBNP)
- CBC w/ Differential (RBC, WBC, Hemoglobin, Hematocrit, Platelets, Neutrophils, Lymphocytes, Monocytes, Eosinophils and Basophils)
- Liver/Renal Function (ALT, ALP, AST, total bilirubin, albumin, total protein, BUN, creatinine)
- TSH
- Panel-Reactive Antibody (PRA) Test (see Appendix D)
- 12 Lead ECG
- Echo (TTE)
- Questionnaire Completion (12 month visit only)

If a subject is unable to safely attend the 3 month and/or 12 month in-clinic follow-up visit(s), the phone follow-up procedures as described in this protocol will replace the in-clinic visits. Medical records will be obtained to provide evidence of the condition that precludes a subject from safely attending the 3 and/or 12 month in-clinic follow-up visit and local medical doctor notes, if available, will be collected.

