#### **4.6 Discontinuation and Withdrawal Subjects**

A subject will be considered a lost to follow-up subject after three documented attempts (the third attempt will be a certified letter) have resulted in failure to contact the parent(s) and/or legal guardian(s).

For the treatment arm, subjects will be discontinued from the study if there is a compromise to the cell product (see Section 5.4.2) following subject enrollment.

Parent(s) and/or legal guardian(s) may decide to withdraw their child from the study at any time during participation in the study. If the parent(s) and/or legal guardian(s) request that their child be withdrawn from the study, the Sponsor will utilize data collected up to that time point but will discontinue future study follow-up assessments. Survival status data will be collected through search of public records by the enrolling site. If a subject has discontinued from active participation but not from the study, standard of care echocardiograms, MRIs, cardiac catheterizations, ECGs, laboratory tests, weight/vitals, and new or worsening conditions that are normally collected for this study will be collected from the subject's medical records, if the parent(s) and/or legal guardian(s) have previously consented to this additional collection of standards of care data. This data is important to ensure there are no safety issues and to monitor for evidence of efficacy in subjects that have decided to withdraw from active participation in the study. Withdrawn subjects and subjects that discontinue from active participation but not from the study will be documented in the applicable eCRF. Documentation must be provided in the subject study chart for any study withdrawal or discontinuation.

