### 7.1 Sample Size Determination

Sample size calculations were performed using alpha = 0.05 and assume equal variance across study arms. With 50 subjects per arm we will have 80% power to detect an effect size as small as 0.57 in difference in cardiac function measures. This is built on the assumption all subjects from both arms have complete data at baseline and 3-month follow-up visits. In the event of attrition or incomplete data in 40% of participants, equal across study arms, the study has 80% power to detect an effect size as small as 0.74 in difference in cardiac function measures.

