### 7.4.3 Short Term Efficacy Analysis

#### Primary Outcome

The primary analysis of the primary outcome apical fractional area change 3 months post Stage II palliative surgery will be done using analysis of covariance (ANCOVA), including a model term for the difference in means between the cell-based therapy and control groups, as well as a model term for apical fractional area change at time of surgery to account for subject baseline condition. In secondary analyses of the primary outcome we will, using interaction terms, fit a model allowing the treatment effect (mean difference between the cell-therapy and control groups) to depend on baseline fractional area change.

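### When a phone visit replaces the 3- or 12-month clinic visit, no echo is required or collected, so the primary FAC measurement is missing for a reason probably related to cardiac condition

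*Combined protocol and SAP*

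**What the plan says.** Section 6.3.2 lists a transthoracic echo at the 3- and 12-month clinic visits. For a child who cannot attend safely, "the phone follow-up procedures as described in this protocol will replace the in-clinic visits". The site then obtains records showing the condition that prevented attendance, and "local medical doctor notes, if available, will be collected".

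The phone procedures are in Sections 6.3.1 and 6.3.3. They cover medication changes, adverse events and, from 6 months on, weight and an annual questionnaire. Section 6.3.3 directs sites to medical records for medications, adverse events and weight. Neither list includes an echo.

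Section 7.4.3 defines the main analysis as an ANCOVA of the "primary outcome apical fractional area change 3 months post Stage II palliative surgery", adjusted for baseline FAC. Section 7.4.4 applies the same model at 12 months. Both outcomes fall on the visits that a phone call may replace.

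Elsewhere the plan does take echoes from routine care. For subjects who leave active participation but not the study, and whose parents consented beforehand, Section 4.6 collects "standard of care echocardiograms, MRIs, cardiac catheterizations, ECGs, laboratory tests, weight/vitals, and new or worsening conditions that are normally collected for this study". Section 6.3.4 takes the Stage III work-up echo from medical records.

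Section 7.3 handles missing data by last observation carried forward (LOCF) where appropriate, and otherwise leaves them missing.

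**The concern.** The substitution is triggered by a condition that makes attendance unsafe. In this population that condition is likely, though not certain, to be linked to right ventricular function. The primary measurement is therefore most likely to be absent where it may be most informative.

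A child still in active follow-up falls between two provisions that would otherwise supply an echo: the one for subjects who have stopped active participation and the one for the Stage III work-up. The site is already requesting this child's records, and a local hospital may already have performed an echo, but nothing tells the site to ask for the images.

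What is at stake is the interpretation of both primary contrasts. The arms are open-label and non-randomised (Section 3.1) and are pre-screened by different routes (Section 4.2), so equal non-attendance for illness cannot be taken for granted.

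**Working it through.** **1. The plan's own figures.** Section 7.1 sets alpha at 0.05 and takes the variances as equal. For complete data its claim is: "With 50 subjects per arm we will have 80% power to detect an effect size as small as 0.57". The reduced-data case is described as "In the event of attrition or incomplete data in 40% of participants, equal across study arms"; there the plan gives a detectable effect of 0.74, again at 80% power. I used a two-sample t-test with equal arms and a noncentral t distribution with 2n − 2 degrees of freedom and noncentrality d × √(n/2). I took alpha as two-sided, because the plan does not state sidedness.

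- n = 50 per arm: detectable d = 0.566 (stated 0.57).
- n = 50 × 0.6 = 30 per arm: detectable d = 0.736 (stated 0.74).
- One-sided alpha (normal approximation) would give 0.497 and 0.642, which do not match.

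Both figures reproduce with two-sided alpha. The allowance enters only as a smaller n that is equal in the two arms. Losing 10% per arm (n = 45) gives 0.597, well inside that allowance. Loss of power is therefore already planned for and is not the point here.

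**2. Which children supply an echo near 3 or 12 months.**

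- Attends the clinic: protocol echo (6.3.2).
- Left active participation, with prior consent: any standard-of-care echo, from records (4.6).
- Active, but visit replaced by phone: no echo named; proof of the precluding condition and local doctor notes only (6.3.2, 6.3.1, 6.3.3).

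Doctor's notes do not fill the gap. Appendix B obtains FAC by tracing end-diastolic and end-systolic areas on the apical 4-chamber images.

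**3. If the value is left missing (complete cases).** Let mT and mC be the shares of each arm without the echo, and D the amount in SD by which those children's FAC lies below that of attenders. Neither is in the documents, so both are assumptions.

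- Each arm mean is overstated by m × D.
- The treatment-minus-control contrast shifts by (mT − mC) × D, or mT × DT − mC × DC if the deficits differ between arms.
- Equal m and equal D: the shift is 0.
- Ten-point imbalance (for example 15% against 5%): 0.10 × 0.5 = 0.05 SD to 0.10 × 1 = 0.10 SD. This is 0.05/0.57 = 9% to 0.10/0.57 = 18% of the planned detectable effect.
- At 15% against 5% with D = 1 (about 42 and 48 children analysed), a nominal 5% test rejects about 7.5% of the time when there is no true effect.

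The sign follows the imbalance: more non-attendance in the treated arm favours the cells, and more in the control arm works against them. These figures ignore baseline adjustment. The ANCOVA removes whatever part of D baseline FAC explains, so they may be too large.

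**4. If LOCF is used.** At 3 months the carried value would be the discharge or baseline FAC; at 12 months it could be the 3-month FAC. The error per child is G = carried value minus true value at the visit, which is positive if function has since fallen. The contrast shifts by mT × GT − mC × GC. This is a different quantity from step 3, and the documents give nothing from which to size it. Section 7.3 does not say when LOCF is appropriate, and Section 7.2 does not say whether a phone visit counts as follow-up data. The plan therefore leaves open which of the two calculations applies.

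**The case against.** The strongest reply is that this is a modest data-collection gap affecting an unknown and possibly very small number of children. Several parts of that reply stand.

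- A reader might infer that the plan excludes the sickest children by rule. The documents do not support this. The trigger is inability to attend safely; sickest is an inference. Nothing forbids an echo: the text fails to require or collect one. The ±14-day window (Section 6.5) lets some children attend later, and LOCF may keep a phoned child in the model.
- A reader might infer that the treatment effect is biased. No rate of non-attendance, FAC deficit or arm difference is given. With equal loss and equal deficit the contrast is unbiased on complete cases.
- A reader might infer that a child who leaves active participation can supply the primary endpoint while an ill child cannot. Section 4.6 is conditional on consent, and it does not say that those images go to the core lab or enter the primary ANCOVA. It shows that a collection route exists, no more.
- Section 7.1 already allows for incomplete data well beyond any plausible loss from this rule.

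The reply fails on one point. Neither the 40% allowance, which assumes equal loss and addresses numbers only, nor LOCF, which can replace a fallen FAC with an earlier one, deals with a measurement missing because of illness. A second caution also stands: echoes done locally for clinical reasons may capture acute decompensation and are not fully equivalent to scheduled ones. The fix allows for this.

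**Conclusion.** The gap is real and should be closed. For a child whose visit is replaced by phone, the plan neither requires nor collects the echo on which both primary analyses rest, and the reason is probably related to cardiac condition. Its missing-data rule then either drops the value or may hide deterioration.

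Confidence is high for the omission and low for its size. Bias in the contrast is possible, not shown: it needs a difference between arms in non-attendance or in its severity. The 0.05 to 0.10 SD shift rests on an assumed 10-point imbalance, an assumed 0.5 to 1 SD deficit, complete-case analysis and no credit for baseline adjustment. Children who die or are transplanted before the visit are a separate problem that this point does not address.

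**What to change.** Amend Section 6.3.2, with a cross-reference to Section 4.6:

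- When a phone visit replaces the 3- or 12-month clinic visit, the site requests any standard-of-care echo already done within the ±14-day visit window, at any hospital, and sends the anonymised DICOM images to the blinded core lab through the Appendix B route.
- If the apical view is readable, that FAC enters the primary ANCOVA in place of LOCF, flagged as local acquisition.
- Echoes from a wider window stated in advance (for example ±30 days) enter a sensitivity analysis only.
- The reason for each replaced visit is recorded and tabulated by arm, so that readers can judge whether the loss is balanced.

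The cost is a short procedural paragraph, image requests for the children concerned and one extra table and sensitivity analysis. It adds no test and does not alter care. The downsides are that some local images will lack the Appendix B view, so recovery will be partial; some will have been done for acute clinical reasons; and consent wording must cover the request.

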#### **6.3.3 6 Month and Bi-Annual Phone Visits:**

- Changes in Concomitant Medications
- AE Assessment
- Questionnaire Completion (to be completed annually following Stage II surgery)
- Weight

At 6 and 18 months post-Stage II surgery, and every 6 months thereafter for up to 4 years (or until the pre-operative Stage III work-up or cardiac transplant), a phone follow-up with the parent(s) and/or legal guardian(s) will include the collection of the above data. In addition to specific questioning by phone follow-up, medical records should be used for documentation of changes in concomitant medications, AE assessment and subject weight.

#### **6.3.4 Pre-Op Stage III Workup Visit:**

- Changes in Concomitant Medications
- AE Assessment
- Physical Exam (including weight)
- Vital Signs (heart rate, blood pressure, oxygen saturation)
- 12 Lead ECG
- Echo (TTE)
- Cardiac Cath (when clinically available)

When the Stage III surgery is scheduled, the date of the Stage III pre-operative work-up and the following standard of care work-up data will be collected from the subject's medical records. If data is not available, the lack of this data will not be considered a protocol deviation. The goal of collecting this data for this study is to evaluate cardiac function that is normally obtained through

standard of care pre-operative testing for the Stage III surgery, without requiring any additional research-only tests/procedures at this time point.

#### **6.4 Questionnaires**

The ITQOL: Infant Toddler Quality of Life Questionnaires and the ASQ-3: Ages and Stages Questionnaires will be administered to participants at baseline and at 12, 24, 36 and 48 months post Stage II surgery for the duration of a subject's participation in the study. Questionnaires should be completed or returned during scheduled in-clinic visits when possible. For non-clinic follow-up visits, questionnaires should be mailed to participants for completion with a self-addressed return envelope. If participants do not return the questionnaires, site staff should administer questionnaires via phone call. This should be documented with in the subject's study binder.

## 6.5 Schedule of Study Tests/Procedures

The below schedule will be followed to complete the study test and procedure requirements.

Schedule of Study Tests and Procedures										
Visit Window	Screening		Enrollment/Treatment			Follow Up				
	Consent 	Baseline/ Pre-Op Workup	Stage II Surgery	Enrollment/ Cell Delivery	Post-Op Hospital Stay 	Hospital Discharge	1-Mo. Phone Visit	3- and 12-Mo. In-Clinic Visit 	6-Mo. And Bi-Annual Phone Visit 	
Visit Window	No more than -30 days	No more than -10 days 	Day 0	Day 0	Day 0 through discharge	No more than 3 days prior 	+/- 7 days	+/- 14 days 	+/- 14 days	No more than 30 days prior
Consent	X									
Assessment of Eligibility				X						
Enrollment				X						
Stage II Surgery			X							
Cell Delivery (Arm A only)				X						
Medical History	X	X	X							
Concomitant Medications	X	X	X			X	X	X	X	
AE Assessment				X	X	X	X	X	X	
Physical Exam^10		X	X		X	X		X	X	
Vital Signs		X	X		X	X		X	X	
Cardiac Markers		X		X		X		X		
CBC w/ Differential		X				X		X		
Liver/Renal Function		X				X		X		
TSH	X					X		X		
PRA test	X							X		
12 Lead ECG	X					X		X	X	
Cardiac MRI	X									
Echo (TTE)	X					X		X	X	
Cardiac Cath.	X								X	
Telemetry				X	X					
Questionnaires	X						X	X		
Study Timeout (Arm A Only)		X								
Procedural Timeout				X						

1 Consent must be obtained prior to commencing any study-related tests/procedures, however standard of care procedures done within 30 days prior to Stage II surgery may be used rather than repeating procedures to collect study data. The subject must appear to meet all study eligibility criteria prior to beginning the consenting process. If the site investigator subsequently determines that the subject is not eligible for the study, the subject will be declared a screen failure and exited from the study.  
 2 If Stage II surgery is rescheduled, Baseline/Pre-Op tests and procedures do not need to be repeated unless the rescheduled surgery will occur more than 30 days after the baseline testing was initially performed.  
 3 Tests/procedures will be performed daily during the hospitalization starting on Day 0. Continuous telemetry is not required on day of hospital discharge.  
 4 Laboratory tests, 12-lead ECG, and echo should be completed within 3 days of the discharge date. However, the laboratory tests, 12-lead ECG, and echo don't have to be repeated if the discharge date changes unexpectedly due to non-cardiac related issues.

- 5 To be conducted at 6 months post-Stage II surgery and every 6 months following the 12 month in-clinic visit for up to 4 years or until pre-operative Stage III work up or cardiac transplant.
- 6 Data to be collected from standard of care Stage III surgery pre-op work up in subject's medical records.
- 7 A subject will be considered enrolled on the study after completion of the procedural time-out.
- 8 Collection of medical history to occur up to enrollment. AE assessments to begin immediately following enrollment.
- 9 During Stage II Surgery hospital stay, changes in concomitant medications will not be recorded.
- 10 Includes weight, except for during post-op hospital stay
- 11 Includes temperature, heart rate, blood pressure and oxygen saturation. Temperature not required at 3 or 12-month in clinic visit.
- 12 Includes the following tests: High Sensitivity Troponin T, CRP, and NT-proBNP. On day 0, only the cardiac biomarker panel (High Sensitivity Troponin T) will be collected at 3 hr  $\pm$  30 min and 6 hr  $\pm$  30 min after enrollment.
- 13 Includes the following tests: RBC, WBC, Hemoglobin, Hematocrit, Platelets, Neutrophils, Lymphocytes, Monocytes, Eosinophils and Basophils
- 14 Includes the following tests: ALT, ALP, AST, Total Bilirubin, Albumin, Total Protein, BUN, and Creatinine.
- 15 Cardiac MRI will only be required at baseline. It is not required at 3 month visit or 12-month follow up. Baseline cardiac MRI should occur within 60 days prior to Stage II surgery.
- 16 When clinically available.
- 17 Questionnaires will be administered to participants at baseline and at 12, 24, 36 and 48 months post Stage II surgery for the duration of a subject's participation in the study.
- 18 Treatment arm only. Must occur within 5 days prior to cell delivery (see Sect. 6.1.2).
- 19 Required for both treatment and control arms (see Sect. 4.3).

## 7 STATISTICAL ANALYSIS PLAN

Sections 3.2 and 3.3 of this protocol provide a full description of the study endpoints.

### 7.1 Sample Size Determination

Sample size calculations were performed using alpha = 0.05 and assume equal variance across study arms. With 50 subjects per arm we will have 80% power to detect an effect size as small as 0.57 in difference in cardiac function measures. This is built on the assumption all subjects from both arms have complete data at baseline and 3-month follow-up visits. In the event of attrition or incomplete data in 40% of participants, equal across study arms, the study has 80% power to detect an effect size as small as 0.74 in difference in cardiac function measures.

### 7.2 Subject Population(s) for Analysis

Only consented and eligible subjects will be used in analysis. Safety analysis will be based upon all subjects who undergo surgery and receive any volume of cell delivery (partial or full) and have follow-up data in the cell-therapy group and all subjects who have follow-up data in the control group. Efficacy analysis will be based upon all subjects who receive full cell delivery and have follow-up data in the cell-therapy group and all subjects who have follow-up data in the control group.

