#### 3.1.2 Subject Evaluation

Once consent has been obtained, subjects will enter the screening phase where a pre-operative baseline work-up will be performed as outlined in Section 6 of this protocol. Following the pre-operative work-up, Stage II surgical repair, and final eligibility confirmation according to the inclusion and exclusion criteria listed in Section 4 of this protocol, the subject will be enrolled on to the trial. Following Stage II surgical repair hospitalization, subjects will enter active follow-up. This includes evaluation in-clinic at 3 and 12-months post-Stage II surgical repair, which will include the collection of imaging data. Phone follow-ups will be conducted at 1 month and 6 months post-Stage II surgery and conducted every 6 months following the 12-month in-clinic visit up to pre-operative work-up for the Stage III Fontan palliative surgery, cardiac transplant or to 4 years post-Stage II surgery, whichever is first.

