#### **4.3 Enrollment/Procedural Timeout**

Enrollment in either arm of this study will occur at the Procedural Timeout. The Procedural Timeout will be conducted in the operating room, by a trained site investigator, following the completion of the Stage II repair. During the Procedural Timeout, a site investigator will confirm all inclusion and exclusion criteria have been met per Section 4.1 of this protocol and document his/her decision to enroll the subject. If the site investigator determines that the subject, in either arm, fails to meet all inclusion and exclusion criteria, the subject will be declared a screen failure (see Section 4.5) and exited from the study. A subject should not be enrolled in either arm of the study if the subject has surgical complications during the Stage II repair that result in, or could be reasonably expected to result in, significantly decreased cardiac function.

For the treatment group, if a subject is determined to be eligible to enroll, the Procedural Timeout will also include confirmation that the subject's identity matches the patient identifiers on the investigational product label, confirmation of the number of injection sites and product volume to be delivered, and confirmation that there aren't any anticipated complications or concerns.

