#### **4.4 Time of Treatment (Treatment Arm Only)**

For subjects enrolled in the treatment arm, thawing of the product and the cell delivery procedure will occur immediately following the Procedural Timeout. A subject is considered treated at the time that cell delivery injections begin. If only a partial cell delivery occurs, the subject will still be considered treated and will be followed as planned according to the procedures described in

Section 6 of this protocol. The cell delivery procedure will be entered in the eCRF and the reason(s) for failing to deliver a full dose, if applicable, will also be documented in the eCRF.

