#### **7.4.5 Safety Analysis**

Adverse Events (AEs) will be described by count and frequency, by body system and severity and groups compared using the chi-square test.

The long-term endpoint regarding arrhythmia events and arrhythmia medication will be analyzed regarding safety. Additional adverse events which will be separated out for analyses of their own will be occurrences of bleeding, to such an extent they would be regarded as AEs, decreased cardiac function, and tumor formation.

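### The Section 7.2 safety set requires follow-up data in both arms, so a child who dies before discharge can be left out of the between-arm adverse-event comparison

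*Combined protocol and SAP*

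**What the plan says.** Section 7.2 opens with a rule for every analysis: "Only consented and eligible subjects will be used in analysis". For safety it then takes treated children who undergo surgery and "receive any volume of cell delivery (partial or full) and have follow-up data in the cell-therapy group", together with "all subjects who have follow-up data in the control group". Neither Section 7.2 nor any other section says what counts as follow-up data.

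Other sections bear on the meaning:

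- Section 3.1.2: "Following Stage II surgical repair hospitalization, subjects will enter active follow-up".
- Section 6.3, the follow-up section, opens with the 1-month phone visit. The post-operative stay (6.2.2) and discharge (6.2.3) sit under Section 6.2, Enrollment.
- Section 6.5, note 8: "AE assessments to begin immediately following enrollment".
- Section 4.4: "A subject is considered treated at the time that cell delivery injections begin".
- Section 7.4.5 describes adverse events by count, frequency, body system and severity, with "groups compared using the chi-square test".
- Section 7.4.1 plans five safety and efficacy interim analyses on everyone enrolled, but says that they follow the statistical analysis plan.

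**The concern.** A safety population should not depend on the patient surviving long enough to be seen again. Several of the delivery risks named in Sections 1.5 and 8.10 are early ones, such as bleeding at the injection site and fever in the first three days, and Section 6.2.1 schedules troponin at 3 and 6 hours after enrollment. If follow-up means the period after the surgical stay, the children who can fall out of the comparison include those with the worst early course.

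The other safety provisions do not put such a child back into the comparison. Three of the four stopping rules in Section 8.11 need an event within 30 days that is classified as definitely related; the fourth is a discretionary rule about patterns. The between-arm table is the planned check that does not depend on a causality call. The long-term transplant-or-death endpoint in Section 3.3 is worded around the time after the 6-month follow-up, so it does not clearly capture early deaths. Section 7.4.2 lets the sponsor decide, at any time after the first interim analysis, that the safety and efficacy endpoints have been met. A table without early deaths could feed that decision.

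**Working it through.** **Reading the text.**

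1. Section 7.2 sets three conditions for the Arm A safety set: surgery, any volume of cells, and follow-up data. The Arm B set requires follow-up data.
2. Sections 3.1.2 and 6.3 place follow-up after the hospital stay, and Section 6 puts the stay and the discharge visit under Enrollment.
3. Take a child who is injected and dies on the ward. The child is treated under Section 4.4 and has adverse events recorded under Sections 6.2.1, 6.2.2 and 6.5, but never reaches anything that Section 6 calls follow-up. On this usage the third condition fails. A control child who dies on the ward fails in the same way.
4. A child discharged alive but lost before the 1-month call also fails, and the in-hospital events already recorded for that child go too.
5. Section 7.4.1 points both ways: everyone enrolled, but according to the analysis plan, which brings Section 7.2 back in.

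**Size (illustration).** The plan gives no figure for the safety set, so there is none to reproduce. The power figures in Section 7.1 concern efficacy and are not affected.

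Inputs: 30 to 50 treated children (Section 2). The in-hospital death rate is not in the documents; p = 1% to 4% is an assumption.

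*Effect of losing one death.* The exact (Clopper-Pearson) upper 95% limit for x events in n is the 97.5th percentile of Beta(x+1, n−x). For x = 0 it is 1 − 0.025^(1/n).

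| Arm A size | Death counted | Child filtered out |
|---|---|---|
| 50 | 1/50 = 2.0%; Beta(2, 49) gives 0.1065, or 10.6% before rounding to four places | 0/49 = 0%; 1 − 0.025^(1/49) = 0.0725, or 7.3% |
| 30 | 1/30 = 3.3%; Beta(2, 29) gives 0.1722, or 17.2% | 0/29 = 0%; 1 − 0.025^(1/29) = 0.1194, or 11.9% |

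*Chance that at least one such death occurs in the arm:* 1 − (1 − p)^n.

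| n | p = 1% | p = 4% |
|---|---|---|
| 50 | 1 − 0.99^50 = 0.395 | 1 − 0.96^50 = 0.870 |
| 30 | 1 − 0.99^30 = 0.260 | 1 − 0.96^30 = 0.706 |

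The expected number of deaths is n × p: 0.5 to 2 among 50, and 0.3 to 1.2 among 30. A control arm of the same size, at the same assumed rate, would give the same figures.

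**The case against.** The strongest reply is that the exclusion is inferred. Section 3.1.2 says when active follow-up begins; it does not define follow-up data. Section 4.4 speaks of following treated children under the procedures of Section 6, which include the hospital stay, and Section 2 records outcomes from the completion of surgery. A lenient analyst could count adverse-event records from Day 0 as follow-up data, and Section 7.4.1 refers to everyone enrolled. This stands in part. It means that such a child can be left out, not that the child certainly is. It does not remove the problem, because membership of the safety set would then turn on how an undefined term is read in an open-label study.

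A reader might infer more than the documents support:

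- *That the filter favors the cells.* Controls face the same condition, so the direction of bias cannot be told.
- *That early delivery harms in general disappear.* In-hospital bleeding, arrhythmia or infarction in a child who later reaches follow-up stays in the comparison. Only children who never reach follow-up are at issue.
- *That Section 7.2 ignores who was treated.* Its any-volume wording is in effect the Section 4.4 test. The added follow-up condition is the fault.
- *That a child who does badly can be ruled ineligible afterwards and removed.* Section 4.3 settles this before injection: at the Procedural Timeout, "a site investigator will confirm all inclusion and exclusion criteria have been met per Section 4.1". No section provides for deciding eligibility again later, and the eligible-subjects rule most naturally separates enrolled children from screen failures. A one-line clarification is enough.

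It is also fair to say that the 1% to 4% range has no source in the documents. Section 4.3 keeps out children whose surgical complications are likely to reduce cardiac function significantly, which may push the rate down.

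**Conclusion.** The concern holds as a defect of wording with a real consequence. As written, and on the protocol's own use of the word follow-up, a child in either arm who dies before discharge or is lost before the first contact can be left out of the between-arm adverse-event comparison, although the data exist. In arms of this size a single child matters: one omitted death removes the only death from the table and lowers the upper 95% limit from 10.6% to 7.3% with 50 treated, or from 17.2% to 11.9% with 30. How likely this is depends on the assumed death rate and on the strict reading of follow-up data; neither is fixed by the documents. Individual reporting, DSMB review and the Section 8.11 rules are not affected.

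**What to change.** In Section 7.2:

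- Remove the follow-up-data condition from the safety set in both arms.
- Define the safety set as all Arm A children in whom injections began, whatever the volume, plus all enrolled Arm B children.
- State that events count from enrollment and include the surgical stay.
- List separately any enrolled Arm A child whose injection was cancelled, for example because the product was compromised (Sections 4.6 and 5.4.2). Such a child is enrolled but not treated.
- As a minor clarification, state that eligibility as documented at the Procedural Timeout stands for the safety set, and that ineligibility discovered later is listed as a deviation.

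In Section 7.4.1, name this set as the population for the interim safety analyses.

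The cost is a change of wording and one extra listing. No new data are needed, because adverse events are already collected from enrollment in both arms. At most, a few more events will appear in the tables.
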